7.7.5. Healthcare resource utilization

Secondary objective 2:

Healthcare resource utilization (HCRU) will be defined as number of outpatient clinic visits, ER visits, hospitalizations, hospital inpatient days, performed procedures, operations, imaging, and laboratory tests. The price will be evaluated for each entry using publicly available price listings.

The absolute number of each HCRU type and the absolute costs associated will be reported. Additionally, the estimates will be scaled to “per-patient” estimates (by dividing the absolute estimates with the number of contributing patients) and to “per patient year” estimates (by dividing the absolute estimates by the number of contributing patient years).

Additionally, assess the HCRU cumulatively over time, i.e. annual costs per patient during the first 5 years from index, each year separately (i.e., the costs during the first year after the diagnosis of advanced/metastatic RCC, during the second year, etc).

No statistical testing for difference between groups will be performed and estimates will be descriptive in nature. However 95% confidence intervals (CI) for the estimates will be derived using bootstrapping over patients.

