- Treatment initiation for mRCC (sunitinib, pazopanib, cabozantinib, ipilimumab, nivolumab)

When analyzing the treatment outcomes, index is defined as the date of the treatment initiation.

End of follow-up (whichever of the following occurs first):

- Death
- Moving outside of HDSF
 - Approximated using data of healthcare contacts; no contacts to specialty care of HDSF within 2 years (patient censored at the last recorded visit)
- End of study (31.12.2021)

Length of follow-up (in years): ('end of follow-up' – 'index' + 1)/365.25

Definitions for characteristics cohort

Index:

- For mRCC patients, same as for the mRCC cohort (i.e. approximated metastasis date)
- For RCC patients, the date of the first record of RCC diagnosis (ICD-10: C64)

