7.3. Variables

Source for all variables is the data lake of HDSF.

Table 2. List of study variables. Abbreviations: PO=primary objective, SO=secondary objective.

Variable	Role/Relevant objective	Operational definition
ICD-10 diagnoses; RCC diagnoses	Patient inclusion/exclusion IMDC risk category	yes/no
ICD-10 diagnoses: co-diagnoses (e.g. renal insufficiency and hypertension)	PO1, SO1	yes/no; co-diagnoses before and after index
Date of birth	Patient inclusion PO1	Date; age defined at index based on birth date
Date of death	End of follow-up PO3	Date
Gender	PO1	Female/male
Home municipality	Patient inclusion End of follow-up	Home municipality at each healthcare contact
Weight	PO1	kg
Height	PO1	m
Body mass index (BMI)	PO1	derived from weight and height
Smoking status (if available in structured format)	PO1	yes/no
Outpatient visits (including emergency room visits)	Patient inclusion and index definition (visits to oncologist) SO2	Date, physician's specialty, type of arrival
Hospitalizations	SO2	Start and end dates
Procedures and operations (including nephrectomy)	PO1 SO1 SO2	Procedure code, date
Medical imaging	SO1 SO2	Imaging code, date
Medications; including - hospital medications - prescriptions	Patient inclusion/exclusion and index definition PO2 PO3 SO1 SO2	Dates, ATC-codes, active substance
Laboratory testing	IMDC risk category PO1	Dates, test id, result
Zubrod/ECOG performance status	IMDC risk category PO1	scale 0-5; converted to Karnofsky
PAD histology (if available in structured format)	PO1	
Staging of RCC, the tumor-node-metastasis (TNM) classification	Patient inclusion and index definition PO1	scale 1-4 (stages)

PFIZER CONFIDENTIAL

Table 3. List of medications for RCC treatment. ATC= Anatomical Therapeutic Chemical.

	Active substance	Brand name	ATC-code at the moment in use	ATC-code previously in use
Oral medications	axitinib	Inlyta	L01EK01	L01XE17
	everolimus	Afinitor	L01EG02	L01XE10
	cabozantinib	Cabometyx	L01EX07	L01XE26
	pazopanib	Votrient	L01EX03	L01XE11
	sorafenib	Nexavar	L01EX02	L01XE05
	sunitinib	Sutent	L01EX01	L01XE04
Intravenous medications	ipilimumab	Yervoy	L01XC11	
	nivolumab	Opdivo	L01XC17	

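### Patient-years for healthcare use stop at the last visit after 2 contact-free years, so the outcome itself decides which zero-use time is counted

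*Combined protocol and SAP*

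**What the plan says.** Secondary objective 2 (section 6.2) concerns specialty-care use in absolute terms, per patient and per patient-year. Section 7.7.5 counts "number of outpatient clinic visits, ER visits, hospitalizations, hospital inpatient days, performed procedures, operations, imaging, and laboratory tests", prices each entry, and forms the per-patient-year figure "by dividing the absolute estimates by the number of contributing patient years". It also plans annual costs per patient for each of the first 5 years from index, with bootstrap confidence intervals.

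Section 7.7.5 does not define patient-years. The only definition of follow-up length is in section 7.2: end of follow-up minus index plus one day, divided by 365.25. Follow-up ends at the first of death, "Moving outside of HDSF" and the end of study on 31.12.2021. Moving is not read from a residence register. It is approximated from contact data as "no contacts to specialty care of HDSF within 2 years (patient censored at the last recorded visit").

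Table 2 in section 7.3 lists "Home municipality at each healthcare contact" as a variable, with the role "Patient inclusion End of follow-up". The rule in section 7.2 does not say how that variable is used.

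**The concern.** The event that closes follow-up is the absence of the thing being measured. A treated mRCC patient who stays in the district but needs no specialty care for the rest of the study is handled as someone who moved on the day of the last visit. The numerator loses nothing, because nothing was used. The denominator loses the whole closing period. For these patients the error can only go upward.

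The rule also depends on the calendar. Two contact-free years cannot be completed within the study window if the last contact falls after 31.12.2019. Those patients keep closing zero-use time that patients with earlier last contacts lose.

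At stake are the per-patient-year rates and costs and the year-by-year costs, most plausibly those for later years from index, when a closing gap has had time to develop. The bootstrap gives no protection, since each resample carries the same shortened follow-up. Section 7.9 does not list this as a limitation, and no sensitivity analysis is planned.

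**Working it through.** **The plan's own figures.** The documents state no patient-years, HCRU rate or expected share of patients cut by the rule. The one figure with stated inputs is the mRCC cohort size in section 7.5: 1,100 × 0.20 = 220 and 1,100 × 0.50 = 550. It reproduces exactly but has no bearing on this point.

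**Effect on the per-patient-year rate.** Let
- f = share of patients cut by the 2-year rule while still resident,
- g = mean deleted gap in years (at least 2 by construction, unless death falls earlier),
- T = mean counted follow-up in years.

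All three are assumptions. With n patients and total use U, the planned rate is U/(nT). With resident gap time restored it is U/(n(T + fg)), because a contact-free gap adds no use. This assumes that no laboratory test or imaging is recorded in the gap without a contact. The ratio of planned to restored rate is 1 + fg/T.

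Example: 100 patients with T = 2 give 200 counted years. If 5 of them lose 3 years each, 15 years are missing, and 215/200 = 1.075.

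| f | g | T | 1 + fg/T |
|---|---|---|---|
| 1% | 2 | 3 | 1.007 |
| 1% | 2 | 2 | 1.010 |
| 5% | 3 | 2 | 1.075 |
| 10% | 3 | 2 | 1.150 |
| 15% | 5 | 1.5 | 1.500 |

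The spread from 0.7% to 50% shows how little the documents constrain the answer. It is not an estimate.

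**Effect on annual cost per patient.** Suppose a year's denominator is the patients still in follow-up, and a share p of living residents has been removed by the 2-year rule with no use in that year. The overstatement is then 1/(1 − p) − 1. For p = 5% this is 1/0.95 − 1 = 5.3%; for p = 10% it is 1/0.90 − 1 = 11.1%. Here p covers only patients cut by the rule, not everyone who happens to have no contact in one year.

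**The calendar edge.** Take index 1.1.2017 and no contact after the last visit.
- Last visit 30.12.2019: the gap to 31.12.2021 is 732 days, or 2.004 years, so follow-up ends at the visit. Counted time = 1,094/365.25 = 2.995 years.
- Last visit 2.1.2020: the gap is 729 days, or 1.996 years, so follow-up runs to 31.12.2021. Counted time = 1,826/365.25 = 4.999 years.

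Three days' difference in the last visit changes the counted time by 2 years.

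**The case against.** The best defence is that ending follow-up at the last observation is a deliberate trade-off, openly labelled an approximation. Someone who has moved still uses care, but the data lake no longer sees it. Counting that time as zero use would bias rates downward. This stands: restoring all gap time is not simply the correct answer, and the net direction across the cohort is not established.

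The population also matters. HCRU covers treated mRCC patients only, and section 5 describes metastatic disease as often fatal. Nothing in the documents suggests that 2-year gaps are common. This stands too.

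Several stronger readings are tempting but not supported:
- *Patients who return after a 2-year gap are also cut.* Censoring at the last recorded visit most naturally cuts only a closing gap, since a returner has a later last visit. The text is at most unclear.
- *Home municipality is collected but ignored.* The 7.2 rule relies on contact data, and Table 2 records municipality at contacts for this purpose, so the two can be read together. What is missing is a statement of how they combine.
- *Using municipality would solve the problem.* It is seen only at contacts and says nothing about a closing gap. It helps only where a later contact exists.
- *Better-risk strata are hit hardest, or early and late index years cannot be compared.* The documents give no data for the former, and no HCRU comparison by index year is planned.

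**Conclusion.** The point holds in a limited form. Patient-years for secondary objective 2 rest on an end-of-follow-up rule driven by the outcome. That rule removes the closing contact-free time of patients who remain resident, and it cannot act on last contacts after 31.12.2019. For the patients affected, per-patient-year and annual estimates are pushed upward; real movers, if their time were kept, would push the other way.

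This assumes that patient-years in section 7.7.5 mean follow-up as defined in section 7.2, which is the natural reading because no other definition exists. The size is unknown and may be small: every percentage above comes from assumed inputs. For a descriptive secondary objective this is a cheap improvement, not a threat to the study's main results.

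**What to change.** 1. **Reconcile section 7.2 with Table 2.** State that a later contact showing a municipality outside HDSF is evidence of a move, and where between the two contacts follow-up then ends. State that a gap is kept as zero-use follow-up when the next contact again shows an HDSF municipality. Say in section 7.7.5 that patient-years follow this definition.
2. **For patients with no later contact, keep the current rule as primary** and repeat the HCRU per-patient-year and annual estimates twice:
   - with follow-up ending at the earliest of death, 31.12.2021 and last visit + 2 years;
   - with follow-up ending at the earlier of death and 31.12.2021.

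   For the patients whom the rule cuts, the current rule and the second repeat are the two extremes. The first repeat lies between them and is not itself a bound, because a patient may stay resident longer than 2 years after the last visit. For last contacts after 31.12.2019 all three end dates coincide, so the runs show the effect of the rule and not every uncertainty about residence.
3. **Report how many patients the 2-year rule cuts.** If there are few, that settles the matter.

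The cost is a short text change, two reruns of the HCRU tables and extra columns in them. Dates of death, contacts and municipality are already requested, so no new data are needed.

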6.2. Secondary objectives

1. Assess morbidity of metastatic RCC including
 - a. co-diagnoses and procedures
 - b. infections and antibiotic use
 - c. antihypertensive use before and after mRCC diagnosis, as applicable

2. Assess speciality care healthcare resource use (absolute, per patient, per patient year)
 - a. cumulatively over time from diagnosis
 - b. by treatment line

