7.2.1. Inclusion criteria

For the **characteristics cohort**, patients must meet all of the following inclusion criteria to be eligible for inclusion:

- Diagnosis of renal cell carcinoma (ICD-10: C64) during 1.1.2010-31.12.2021
- Age at least 18 years at index.
- Resident of HDSF at index.

For the **mRCC cohort**, patients must meet the following inclusion criteria in addition to the above criteria to be eligible for inclusion:

- metastatic RCC during 1.1.2010-31.12.2021; defined as
 - ICD-10 diagnosis code for metastasis (C77*-C79*), or
 - AJCC stage 4, or
 - AJCC stage data potentially not available for all patients
 - a visit to oncologist (specialty code 65) with RCC as main diagnosis, or
 - In Finland, the ICD-10 codes for metastatic disease are rarely used. In contrast, RCC patients visit oncologist, when and only when disease metastasises and therefore, the visit can be used as a proxy to a metastatic disease.
 - initiation of treatment for mRCC

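### The annual cost per patient has no defined denominator and no rule for years cut off by censoring, and the separate annual figures do not give the cumulative use that secondary objective 2a asks for

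*Combined protocol and SAP*

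**What the plan says.** Section 6.2 sets secondary objective 2 as specialty-care resource use in absolute terms, per patient and per patient year. Part 2a asks for it "cumulatively over time from diagnosis".

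Section 7.7.5 defines two scalings. The per-patient figure is obtained "by dividing the absolute estimates with the number of contributing patients"; the per-patient-year figure "by dividing the absolute estimates by the number of contributing patient years". It then explains the cumulative assessment as "annual costs per patient during the first 5 years from index, each year separately", counted from the diagnosis of advanced or metastatic disease. Confidence intervals come from a bootstrap over patients, with no testing between groups.

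Section 7.2.1 admits patients with "metastatic RCC during 1.1.2010-31.12.2021". Under section 7.2, follow-up ends at death, at 31.12.2021, or, for patients presumed to have moved away, at the last recorded visit. Sections 7.2.3 and 7.7 stratify these results by IMDC risk category.

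The plan does not say who contributes to a given year, which of the two denominators the annual series uses, how a year cut short by censoring is counted, or how survival enters a cumulative figure.

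**The concern.** Two separate problems arise.

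The first is censored part-years. A patient indexed in mid-2021 has about half of year 1 on record. If that patient counts as one whole patient, the denominator is complete and the cost is not. The same happens in each later year and to presumed movers. Death is different: cost after death is truly zero, so a death within the year does not bias cost per patient.

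The second is accumulation. An annual mean among patients who reach the start of a year is conditional on reaching it. Five such means describe five shrinking groups, and their plain sum is not what an average patient costs over five years from diagnosis.

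At stake is whether objective 2a gets a valid answer, overall and by IMDC category. The bootstrap does not help, because it measures sampling error around whatever is estimated and does not remove bias from censoring.

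**Working it through.** **Inputs from the plan.** Entry window of 12 years, 1.1.2010-31.12.2021 (section 7.2.1); administrative end on the day entry closes (section 7.2); annual series for years 1 to 5 (section 7.7.5). The only computed figure in the plan is the cohort size in section 7.5, which reproduces: 1,100 × 0.20 = 220 and 1,100 × 0.50 = 550. The treated cohort used for this objective will be smaller. The plan states no cost, survival or censoring figure.

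**Assumptions not in the plan.** Uniform entry; exponential survival with median 1, 2, 3 or 5 years; cost of 1 unit per year alive; no loss from moving away.

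**Part-years, before deaths.** Possible follow-up is uniform on 0 to 12 years, so 5/12 = 42% of patients cannot have five years. Of those who can start year k, a share 1/(13 − k) are cut off within it and lose half a year on average. The shortfall is half that share.
- Year 1: 1/12 = 8.3% cut off; shortfall 4.2% (observed 11.5/12).
- Year 5: 1/8 = 12.5% cut off; shortfall 6.3% (observed 7.5/8).

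With deaths included, simulation of 2,000,000 patients per scenario gives a shortfall of 3.7-4.1% in year 1 and 5.4-6.1% in year 5 across the four medians.

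**Accumulation.** With λ = ln 2 / median, the true 5-year mean cost is (1 − e^(−5λ))/λ. For a median of 3 years, λ = 0.231 and the true value is 2.97. The simulated annual means per patient starting each year are 0.857, 0.854, 0.850, 0.844 and 0.839, against a true 0.893 in each year.
- Plain sum: 4.25 with unrounded means. 4.245/2.966 = 1.43, so 43% too high.
- Weighted by survival to the start of each year (1, 0.794, 0.630, 0.500, 0.397): 0.857 + 0.678 + 0.536 + 0.422 + 0.333 = 2.83, about 5% low. That remainder is the part-year shortfall.

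| Assumed median survival | True 5-year cost | Plain sum | Error | Survival-weighted sum |
|---|---|---|---|---|
| 1 year | 1.40 | 3.44 | +146% | 1.34 |
| 2 years | 2.38 | 4.02 | +69% | 2.27 |
| 3 years | 2.97 | 4.25 | +43% | 2.83 |
| 5 years | 3.61 | 4.44 | +23% | 3.43 |

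In the runs checked (medians 2, 3 and 5 years), adding a one-unit cost at death leaves the error percentages essentially unchanged.

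**Per-patient-year rates.** These recover the constant cost rate of 1 despite part-years. Summing five gives 5.0, which is the cost of five years lived: 5.0/3.61 is 39% too high at a 5-year median, and 5.0/1.40 is 258% too high at 1 year (unrounded values).

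**The case against.** The strongest reply is that section 7.7.5 itself explains the cumulative assessment as separate years, so no sum is planned and the yearly cost among patients still followed is a legitimate descriptive quantity. The sentence on annual costs also names no denominator. The patient-year scale stands in the stem of objective 2, above part 2a, and allows for part-observed time. The analysis is descriptive, and 4-6% is small.

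Much of this stands, and it limits what can be claimed. A reader might infer any of the following, and the documents support none of them:
- **That yearly costs are too low whatever the denominator.** The term contributing is undefined. If it means patients with a record in that year, zero-cost patients drop out and the figure is pushed upward.
- **That year 5 is about 37% low.** This follows only if the whole cohort is the denominator in every year (1 − 7.5/12 = 37.5% before deaths). That is a strained reading, because recently indexed patients cannot contribute to year 5.
- **That the plan will report a total 69% too high.** No addition is stated, and 69% is one assumed survival case in a range of 23% to 146%.

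The reply does not close the gap. The annual figures are labelled per patient, and the only per-patient rule stated makes no allowance for censored time. A patient-year rate for each year would settle the part-year problem but not the cumulative one. If no sum is intended, objective 2a has no cumulative estimator.

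**Conclusion.** The point holds as a gap in specification with a measurable consequence. On the natural reading, with patients under follow-up at the start of the year as denominator, annual costs are about 4% low in year 1 and 5-6% low in year 5. This rests on the plan's dates, uniform entry and constant cost while alive, and depends little on survival. Presumed movers are not in the figure.

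The separate annual costs do not deliver objective 2a. Anyone who adds them without survival weighting overstates 5-year cost by 23% to 146%, depending on assumed median survival. The error grows as survival shortens, and the IMDC category is built from predictors of poor survival. Added costs would therefore be most inflated in the poor-prognosis strata, which distorts comparison between strata as well as the overall level.

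For a secondary, descriptive objective this should be corrected, but it does not threaten the primary results.

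**What to change.** In section 7.7.5:
1. For year k, define the denominator as patients alive and under follow-up at the start of that year.
2. Estimate mean cost in year k with inverse-probability-of-censoring weights within the year. Restricting year k to patients indexed at least k years before 31.12.2021 is simpler, but does not deal with presumed movers.
3. Report 5-year cumulative cost as the sum over years of Kaplan-Meier survival to the start of the year times that year's mean, overall and by IMDC category. State that the annual figures are conditional on reaching the year and are not to be added directly.
4. Run the whole procedure, including the weights and the Kaplan-Meier step, inside the planned patient bootstrap.

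The index, death and censoring dates are already required, and Kaplan-Meier estimation is already planned in section 7.7.3. The cost is modest programming and wider intervals in years 4-5.

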7.7.6. Changes in coding practices over time

Exploratory objective 1:

Assess changes in coding practices as a proportion of patients with data available respect to the diagnosis year of advanced/metastatic RCC. Variables of interest include but are not limited to

- structured IMDC risk score
- ICD-10 diagnosis for metastatic disease (C77*-C79*)

Other aspects of changes in coding practices may also be analyzed, if reasonable.

7.8. Quality control

Internal quality will be assured by consulting a clinical expert on data integrity, clinical relevance, and plausibility of the results.

A quality control will be performed, whereby all data will be sanity checked by the allocated data scientist(s). This control includes e.g. data coverages, number of individuals and data rows, changes as a function of time and checks for systematic gaps on data coverage and outliers in the data. Additionally, all the results will be sanity checked with a clinical expert and study team for plausibility and clinical relevance, and especially in case of unexpected results, both analytical methods and data will be discussed and validated with the whole Medaffcon analytics team.

All R scripts to process and analyze the data will be saved, and there is version control and external back-ups for the scripts. At the end of the study, all scripts will be archived to assure analysis reproducibility, and plausible later audits (by client and/or from scientific publication side).

7.9. Limitations of the research methods

All the data is recorded by the hospital during everyday practice and most of the data is stored in structured format. Therefore, rather high quality of the data is expected. However, as with all RWD, it is plausible to have erroneous entries. Also due to the retrospective nature of the study, missing and/or incomplete data is expected in some of the medical records. Patients' records will not be excluded because of missing values, and missing data will not be imputed, i.e. the data will be analyzed as they are recorded in the electronic medical records. The proportion of missing values per variable will be reported.

The treatment lines will be defined based on the medication data and therefore, misclassification of treatment lines is possible. However, the start and end dates of each main drug are expected to be recorded rather precisely, and the clinician PPD will be consulted when constructing the treatment lines. Thus, the majority of the treatment lines are expected to be defined correctly.

